8.1.1. Study Objectives and Endpoints

Primary Objective

- To evaluate the safety profile of CFDA approved sunitinib in treating Chinese patients with progressive, unresectable, advanced or metastatic well-differentiated, pancreatic neuroendocrine tumors.

Secondary Objectives

- To assess progression-free survival (PFS).
- To assess PFS by clinical judgment.
- To assess overall survival (OS).
- To estimate 5-year survival rate.

Primary Endpoints

Every observed and reported adverse event and all associated laboratory abnormalities, regardless of the causal relationship with the study drug, will be recorded as an adverse event in the CRF. At each visit, patients will be questioned with non-leading questions for example as follows:

"Have you had any health problem since the last visit?"

Assessment of adverse events and SAE data will include type, incidence, severity (graded by the National Cancer Institute [NCI] Common Terminology Criteria [CTCAE] version 4, see [ANNEX 2](#)) and relatedness; and laboratory abnormalities.

Adverse events of particular interest are as follows:

- Infections;
- Cardiac and vascular;

- Skin and subcutaneous tissue;

The most common skin and subcutaneous tissue related adverse events of interest are rash (includes erythematous, macular, or scaly rash), hand foot syndrome (HFS) or palmoplantar erythrodysesthesia (PPE), dry skin and skin discoloration

- Gastrointestinal;
- Psychiatric and nervous system;
- Musculoskeletal;
- Thyroid function;
- General disorders;
- Others;
- laboratory abnormalities:

1. Haematologic: hemoglobin, platelet count, white blood cell count, neutrophile granulocyte count.
2. Non Haematologic: total bilirubin, ALT (Alanine Transaminase), AST (Aspartate Transaminase), alkaline phosphatase, GGT (Gamma-Glutamyl Transferase), total protein, albumin, BUN (Blood Urea Nitrogen), creatinine, uric acid, glucose, hypocalcemia, hyponatremia, hypophosphatemia, hypokalemia.

Secondary Endpoints

Progression-Free Survival:

Investigator assessed PFS according to RECIST 1.1.6 PFS is defined as the time from the start of sunitinib treatment to first document of objective tumor progression or death due to any cause, whichever occurs first.

Progression-Free Survival by clinical judgment:

PFS by clinical judgment is defined as the time from the start of sunitinib treatment to first document of objective tumor progression, or first time tumor progression diagnosed by investigator based on clinical judgment, or death due to any cause, whichever occurs first.

Overall Survival Time:

Overall Survival (OS) is defined as the time from the start of sunitinib treatment to documentation of death due to any cause.

5-Year Survival Rate:

5-year survival rate is defined as the percentage of patients who stay alive till after 5 years from the start of sunitinib treatment.

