8.3.3. Safety Data Collection (From First Dosage to Last Dosage of Sunitinib)

- Physical examination:
 - examination of major body systems, such as general appearance, throat, neck, thyroid, lungs, heart, breasts, abdomen, musculoskeletal, extremities, skin, lymph nodes, neurological, others, ECOG performance status, body weight, height, and vital signs (eg, temperature, blood pressure, and heart rate).
- All AE and SAE data

Data collection includes:

1. Infections.
2. Cardiac and vascular:
 - 12-lead ECG.
 - MUGA or ECHO for LVEF assessment (if applicable, within current clinical practice).
3. Skin and subcutaneous tissue:
 - The most common skin and subcutaneous tissue related adverse events of interest are rash (includes erythematous, macular, or scaly rash), hand foot syndrome (HFS) or palmoplantar erythrodysesthesia (PPE), dry skin and skin discolouration.
4. Gastrointestinal.
5. Psychiatric and nervous system.
6. Musculoskeletal.
7. Thyroid function (if applicable, within current clinical practice):
 - Thyroid function testing (see [ANNEX 3](#) for laboratory tests).
8. General disorders.
9. Others.

10. laboratory abnormalities:

- Haematologic: hemoglobin, platelet count, white blood cell count, neutrophile granulocyte count.
- Blood chemistry: total bilirubin, ALT (Alanine Transaminase), AST (Aspartate Transaminase), alkaline phosphatase, GGT (Gamma-Glutamyl Transferase), total protein, albumin, BUN (Blood Urea Nitrogen), creatinine, uric acid, glucose, hypocalcemia, hyponatremia, hypophosphatemia, hypokalemia. Urine protein assessment, if applicable (see [ANNEX 3](#) for laboratory tests).

This data will be reported on the appropriate electronic CRF and Adverse Event Monitoring (AEM) forms during treatment with sunitinib.

For the subjects who have already taken sunitinib within the past 6 months (26 weeks) and will continue sunitinib therapy, these key element data, such as demographic data, medical history, medication history, physical examination, 12 lead Electrocardiogram (ECG), hematology and blood chemistry, tumor imaging, will be collected after their sunitinib treatment.

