10. MANAGEMENT AND REPORTING OF ADVERSE EVENTS/ADVERSE REACTIONS

10.1. Requirements

The table below summarizes the requirements for recording safety events on the case report form and for reporting safety events on the non-interventional study (NIS) adverse event monitoring (AEM) Report Form to Pfizer Safety. These requirements are delineated for three types of events: (1) serious adverse events (SAEs); (2) non-serious AEs (as applicable); and (3) scenarios involving drug exposure, including exposure during pregnancy, exposure during breast feeding, medication error, overdose, misuse, extravasation, and occupational exposure. These events are defined in the section “Definitions of safety events”.

Safety event	Recorded on the case report form	Reported on the NIS AEM Report Form to Pfizer Safety within 24 hours of awareness
SAE	All	All
Non-serious AE	All	None
Scenarios involving exposure to a drug under study, including exposure during pregnancy, exposure during breast feeding, medication error, overdose, misuse, extravasation; lack of efficacy; and occupational exposure	All (regardless of whether associated with an AE), except occupational exposure	All (regardless of whether associated with an AE)

For each AE, the investigator must pursue and obtain information adequate both to determine the outcome of the adverse event and to assess whether it meets the criteria for classification as a SAE (see section "Serious Adverse Events" below)

Safety events listed in the table above must be reported to Pfizer within 24 hours of awareness of the event by the investigator **regardless of whether the event is determined by the investigator to be related to a drug under study**. In particular, if the SAE is fatal or life-threatening, notification to Pfizer must be made immediately, irrespective of the extent of available event information. This timeframe also applies to additional new (follow-up) information on previously forwarded safety event reports. In the rare situation that the investigator does not become immediately aware of the occurrence of a safety event, the investigator must report the event within 24 hours after learning of it and document the time of his/her first awareness of the events.

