10.2. Definitions of Safety Events

10.2.1. Adverse Events

An AE is any untoward medical occurrence in a patient administered a medicinal product. The event need not necessarily have a causal relationship with the product treatment or usage. Examples of adverse events include but are not limited to:

- Abnormal test findings (see below for circumstances in which an abnormal test finding constitutes an adverse event);
- Clinically significant symptoms and signs;
- Changes in physical examination findings;
- Hypersensitivity;
- Lack of efficacy;
- Drug abuse;
- Drug dependency.

Additionally, for medicinal products, they may include the signs or symptoms resulting from:

- Drug overdose;
- Drug withdrawal;
- Drug misuse;
- Off-label use;

- Drug interactions;
- Extravasation;
- Exposure during pregnancy;
- Exposure during breast feeding;
- Medication error;
- Occupational exposure.

Abnormal test findings

The criteria for determining whether an abnormal objective test finding should be reported as an adverse event are as follows:

- Test result is associated with accompanying symptoms, and/or
- Test result requires additional diagnostic testing or medical/surgical intervention, and/or
- Test result leads to a change in study dosing or discontinuation from the study, significant additional concomitant drug treatment, or other therapy, and/or
- Test result is considered to be an adverse event by the investigator or sponsor.

Merely repeating an abnormal test, in the absence of any of the above conditions, does not constitute an adverse event. Any abnormal test result that is determined to be an error does not require reporting as an adverse event.

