6.2. Safety Endpoints

Primary safety outcomes include the frequency of adverse events and serious adverse events. Adverse events of particular interest are as follows:

- *Infections and infestations.*
- *Cardiac and vascular.*
- *Skin and subcutaneous tissue:*
 - *The most common skin and subcutaneous tissue related adverse events of interest are rash (includes erythematous, macular, or scaly rash), hand foot syndrome (HFS) or palmo plantar erythrodysesthesia (PPE), dry skin and skin discoloration.*

- *Gastrointestinal.*
- *Psychiatric and nervous system.*
- *Musculoskeletal.*
- *Thyroid function.*
- *General disorders.*
- *Others.*
- *Laboratory abnormalities:*
 - *Haematologic: hemoglobin, platelet count, white blood cell count, neutrophile granulocyte count.*
 - *Non Haematologic: total bilirubin, ALT (Alanine Transaminase), AST (Aspartate Transaminase), alkaline phosphatase, GGT (Gamma-Glutamyl Transferase), total protein, albumin, BUN (Blood Urea Nitrogen), creatinine, uric acid, glucose, hypocalcemia, hyponatremia, hypophosphatemia, hypokalemia.*

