8.2. Statistical Analyses

8.2.1. Analysis of Primary Safety Endpoints

Safety endpoints will be summarized for the safety analysis set.

Safety data, such as AEs, vital signs, ECOG status, laboratory data, physical examination etc., will be tabulated and listed according to Pfizer’s standard reporting algorithms. Medical Dictionary for Regulatory Activities (MedDRA) and WHO drug dictionary will be used. The severity of all AEs will be coded using NCI CTCAE Version 4.0.

For the adverse events of particular interest, 95% CI will be presented using the exact method (Clopper-Pearson interval).

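### The documents do not settle when a laboratory abnormality counts as an adverse event, so laboratory-term AE frequencies can differ by site

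*Protocol*

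**What the plan says.** Four places in the protocol and two in the SAP bear on this.

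- **Protocol 8.1.1 (Primary Endpoints).** The sentence opens with every AE that is observed and reported, then adds that "all associated laboratory abnormalities, regardless of the causal relationship with the study drug, will be recorded as an adverse event in the CRF". It sets no threshold. The same section lists laboratory abnormalities, parameter by parameter, among the AEs of particular interest.
- **Protocol 8.3.3.** Laboratory abnormalities are item 10 under the heading for all AE and SAE data, again with no criterion. The section closes: "This data will be reported on the appropriate electronic CRF and Adverse Event Monitoring (AEM) forms during treatment with sunitinib".
- **Protocol 10.1.** Its scope includes CRF entry, not only reports to the sponsor: "The table below summarizes the requirements for recording safety events on the case report form". All non-serious AEs go on the CRF, and the reader is sent to the definitions in 10.2.
- **Protocol 10.2.1.** "The criteria for determining whether an abnormal objective test finding should be reported as an adverse event are as follows". Any one of four criteria is enough: symptoms; a need for more testing or for treatment; a change in dosing, discontinuation or significant added therapy; or "Test result is considered to be an adverse event by the investigator or sponsor". It then adds: "Merely repeating an abnormal test, in the absence of any of the above conditions, does not constitute an adverse event".
- **SAP 6.2** (matching Protocol 8.7). "Primary safety outcomes include the frequency of adverse events and serious adverse events". The laboratory parameters are again listed among the AEs of particular interest.
- **SAP 8.2.1.** "For the adverse events of particular interest, 95% CI will be presented using the exact method (Clopper-Pearson interval". Laboratory data are also tabulated, but the section does not say whether the laboratory items of particular interest come from AE entries or from measured values.

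**The concern.** A site working from 8.1.1 and 8.3.3 could enter every out-of-range value as an AE. A site working from 10.2.1 would enter only those that meet a criterion. Both would believe they were following the protocol, and both would be filling in the same CRF field.

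The laboratory items belong to the primary outcome and receive exact 95% intervals. The study has a single arm, so no control group shares the recording rule and offsets its effect: the absolute frequency is the result. A pooled laboratory-term rate would then reflect the mix of sites as well as the patients, and the exact interval would not show it, because that interval covers sampling error only.

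**Working it through.** **1. Do the two rules govern the same record?** Yes. 8.1.1 names the CRF. 10.1 applies the section 10 definitions to CRF recording as well as to reports to the sponsor. So 10.2.1 cannot be set aside as a reporting rule only.

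**2. Do they differ?** That depends on the word *associated* in 8.1.1, which is not defined.

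| Reading of 8.1.1 | Effect | Support in the text |
|---|---|---|
| Narrow: abnormalities that accompany an AE | Largely agrees with 10.2.1 | The grammar of the sentence, which names the AE first |
| Broad: every laboratory abnormality | Wider than 10.2.1 | Unqualified listings in Protocol 8.1.1, 8.3.3 and 8.7 and SAP 6.2 |

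No precedence clause chooses between them.

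**3. How large could the effect be?** The plan states no laboratory rate, so there is no figure to reproduce and the rates below are assumptions. The one input from the documents is N of about 100 (Protocol 8.5: about 20 patients a year × 5 years = 100).

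Let L be the number of patients with a given abnormality and q the share of them who meet a 10.2.1 criterion. The AE count is L under the broad rule and L × q under 10.2.1. The two-sided 95% Clopper-Pearson limits for x of n are:

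- lower = 2.5% quantile of Beta(x, n − x + 1)
- upper = 97.5% quantile of Beta(x + 1, n − x)

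With n = 100 (percent, 95% CI):

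| L | Broad rule | q = 25% | q = 50% | q = 75% |
|---|---|---|---|---|
| 20 | 20 (12.7–29.2) | 5 (1.6–11.3) | 10 (4.9–17.6) | 15 (8.6–23.5) |
| 40 | 40 (30.3–50.3) | 10 (4.9–17.6) | 20 (12.7–29.2) | 30 (21.2–40.0) |
| 60 | 60 (49.7–69.7) | 15 (8.6–23.5) | 30 (21.2–40.0) | 45 (35.0–55.3) |

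At q = 100% the two rules give the same result. At q = 25% no pair of intervals overlaps; at q = 75% all three pairs do.

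**4. What if sites differ?** Let s be the share of patients at sites using the broad rule. With L = 40 and q = 50%, and both the same across sites, the pooled rate is 40s + 20(1 − s). This gives 20% at s = 0, 30% at s = 0.5 and 40% at s = 1.

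**The case against.** The strongest reply is that this is loose wording and not two competing rules. Read from its start, the 8.1.1 sentence ties *associated* to the AE just named. Its evident purpose is to record events whatever their cause, not to set a threshold. An endpoint section need not repeat definitions, and 10.1 sends the reader to 10.2 for them. 10.2.1 is also not purely restrictive: because judgement alone is enough, a site that records broadly can still comply. Finally, laboratory data are tabulated anyway, so rates from values can be obtained whatever is entered as an AE.

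Much of this stands. A reader might infer a flat contradiction; the documents do not support that, because the narrow reading is available and removes most of the conflict. A reader might also infer that aligning 8.1.1 with 10.2.1 would make sites comparable. It would not do so fully, since investigator judgement remains a sufficient criterion. And an asymptomatic value that appears in both an AE table and a laboratory table is not counted twice within either estimate.

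What does not stand is that the reply settles the matter. The listings in 8.3.3, 8.7 and SAP 6.2 carry no criterion, and a site could reasonably follow them. That values can be tabulated does not make them the stated source for the laboratory items that receive exact intervals.

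**Conclusion.** The point holds as an unresolved ambiguity on one component of the primary outcome, together with an unnamed data source in SAP 8.2.1. It is worth correcting.

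On the middle assumption of 40 affected patients in 100, with 25–75% meeting 10.2.1, a laboratory-term incidence would be 40% under the broad rule and 10% to 30% under 10.2.1, a gap of 10 to 30 percentage points. The gap is zero if every abnormality meets a criterion. All of these rates are assumed, and they compare the extremes at which every site follows the same rule; a mixture falls between.

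A reader might infer that the primary AE frequencies as a whole are unreliable. The documents do not support that. The effect falls on laboratory-term AEs and on AE counts. The proportion of patients with any AE may move less, and SAE frequencies should move little because seriousness has its own definition in Protocol 10.2.2. Nor should non-overlapping intervals be taken as a finding: whether they overlap follows from the rates assumed.

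**What to change.** 1. **Protocol 8.1.1 and 8.3.3.** Add a cross-reference to 10.2.1 in both, so that one AE recording rule applies. Changing 8.1.1 alone would leave the unqualified list in 8.3.3 in place.
2. **SAP 6.2 and 8.2.1.** State that the laboratory-abnormality outcome is derived from collected laboratory values graded by CTCAE version 4. Use as denominator the patients with a post-baseline result for that parameter, show the number tested beside the safety-set N, and present it separately from AE-term tables. The outcome then no longer depends on the recording rule a site used, which step 1 alone cannot achieve.
3. **Reporting.** Give laboratory-term AE rates with a note that entries may reflect mixed rules.

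**Cost.** A protocol amendment and a SAP amendment; Protocol 8.7 already foresees a protocol amendment for major changes to primary endpoint definitions or analyses. The values are already collected, so no new data are needed. The denominator will differ from the safety set, and because testing follows routine practice it will vary by parameter, so the number tested must be visible. Data collection was planned to start on 15 December 2014, so existing AE entries may follow either rule. The amendment does not repair those, which is why the note in step 3 is needed.

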8.2. Setting

8.2.1. Population

The Chinese adult (Age \geq 18 years) who are diagnosed well-differentiated pNET by histologically or cytologically and unresectable (as assessed by the investigator) or metastatic pNET documented on a scan is the target population. This NI study plans to enroll these patients who are eligible and willing to participate in this study.

8.2.2. Duration of Subject Participation

The frequency of the NI study visits may be conducted following the local medical advice and it is usually once in 1 or 2 months. In the post-treatment follow-up visit, in the event a subject is unable to return to the clinic for the visit, telephone contact with the subject to assess adverse events and concomitant medications and treatments is expected and is to be conducted at least 28 calendar (+10 days). If the subject withdraws from the study, and also withdraws consent for disclosure of future information, no further evaluations should be performed, and no additional data should be collected. The sponsor may retain and continue to use any data collected before such withdrawal of consent. All subjects who don't withdraw from the study will be followed for survival status (if permitted).

8.2.3. Definitions of Loss to Follow-up

The investigator should attempts to contact the subject. After three unsuccessful attempts to contact the subject on different dates, the subject should be considered lost to follow-up. All attempts should be documented in the Subject Summary CRF.

8.2.4. Definitions of Subject Withdrawal

Subject may be withdrawn from treatment in the case of:

- Subject lost to follow-up.
- Withdrawal of subject consent (cessation of follow-up).

8.2.5. Inclusion criteria

Patients must meet all of the following inclusion criteria to be eligible for inclusion in the study:

Patient's eligibility should be reviewed and documented by an appropriately qualified member of the investigator's study team before subjects are included in the study.

1. Evidence of a personally signed and dated informed consent document indicating that the subject (or a legally acceptable representative) has been informed of all pertinent aspects of the study.
2. Subjects who will accept sunitinib therapy, or subjects who have already taken sunitinib within the past 6 months (26 weeks) and will continue sunitinib therapy, and are willing to follow up visits within current clinical practice.
3. Histologically or cytologically proven diagnosis of well-differentiated pancreatic neuroendocrine tumors (according to WHO 2000 classification).²
4. Unresectable (as assessed by the investigator) or metastatic disease documented on a scan.
5. Age ≥ 18 years.

8.2.6. Exclusion Criteria

Patients meeting any of the following criteria will not be included in the study:

1. Patients with poorly-differentiated pancreatic neuroendocrine tumors (according to WHO 2000 classification).²

8.3. Variables

This study will collect and analyze the safety and efficacy data from approximately 100 eligible subjects from the time of first subject first visit to the time the study is closed. Since this is primarily an observational study, there are no patient visits specified by virtue of this protocol.

8.3.1. Baseline Data Collection (Day 0)

The baseline data must be performed prior to the start of sunitinib treatment :

- For the subjects who haven't taken sunitinib and will accept sunitinib therapy, they (or a legally acceptable representative) sign on current Institutional Review Board (IRB)/Independent Ethics Committee (IEC) approved informed consent document.
- Demographic data:
 - Date of birth, height, weight, race.
- Medical history:
 - Cancer history treatment, tumor Ki-67 index(assessment based on previous tumor biopsy results or previous surgical resections to be provided.), response to treatment, ongoing symptoms/events.
- Medication history:

- History of other disease processes (active or resolved), concomitant illnesses and treatments.
- Physical examination:
 - Examination of major body systems, such as general appearance, throat, neck, thyroid, lungs, heart, breasts, abdomen, musculoskeletal, extremities, skin, lymph nodes, neurological, others, ECOG performance status, body weight, height, and vital signs (eg, temperature, blood pressure, and heart rate).
- Hematology and blood chemistry (see [ANNEX 3](#) for laboratory tests):
 - Haematologic: hemoglobin, platelet count, white blood cell count, neutrophile granulocyte count.
 - Blood chemistry: total bilirubin, ALT (Alanine Transaminase), AST (Aspartate Transaminase), alkaline phosphatase, GGT (Gamma-Glutamyl Transferase), total protein, albumin, BUN (Blood Urea Nitrogen), creatinine, uric acid, glucose, hypocalcemia, hyponatremia, hypophosphatemia, hypokalemia.
- 12-lead ECG.
- If applicable, tumor imaging should be performed as appropriate within current clinical practice:
 - CT scans/MRI of chest, abdomen, pelvis, brain and bone scan, in addition to any other applicable sites of disease.

For the subjects who have already taken sunitinib within the past 6 months (26 weeks) and will continue sunitinib therapy, these key element baseline data, such as demographic data, medical history, medication history, physical examination, 12 lead Electrocardiogram (ECG), hematology and blood chemistry, tumor imaging, will be collected prior to their sunitinib treatment after the subject or their legal representative has provided informed consent.

8.3.2. Treatment and Efficacy Data Collection (From First Dosage to Last Dosage of Sunitinib)

For the subjects who have already taken sunitinib within the past 6 months (26 weeks) and will continue sunitinib therapy, they (or a legally acceptable representative) sign on current Institutional Review Board (IRB)/Independent Ethics Committee (IEC) approved informed consent document on the day that they decide enrollment this study.

- Administration of sunitinib:
 - Dose reduction or escalation for any reason.
- Tumor imaging, if applicable:

- CT scans/MRI of chest, abdomen, pelvis, brain and bone scan, in addition to any other applicable sites of disease.
- Concomitant medications and treatments.

